Operational Changes during the COVID-19 Pandemic	For the duration of the COVID-19 pandemic and in response to directives from the Vice Chancellor for Research and the UCI Human Research Protections Program, the Chao Family Comprehensive Cancer Center's Stern Center for Cancer Clinical Trials and Research will be modifying operations as outlined in Interim Standard Operating Procedure "Clinical Trial Enrollment and Operations during the COVID-19 Pandemic" dated 06April2020. In addition, the University of California Irvine Medical Center Pharmacy Services has issued guidance regarding the shipment of Investigational Drug Product directly to clinical trial participants when in-person clinic visits are not feasible or recommended. This new process is described in "Investigational Drug Services: Emergent Shipment of Investigational Product Policy" dated 23March2020. Current versions of these SOP and Policy documents may be obtained at the following URL: \hs.uci.edu\myshare\Cancer Center Research\COVID-19\Research\SOPs and Guidelines	
Methodology	Open label, single arm	
Study Duration	3 years	
Study Center(s)	Single Center	
Objectives	Primary objective: To estimate the efficacy of cabozantinib combined with pembrolizumab in patients with advanced gastric and gastroesophageal adenocarcinoma (GC) Primary Endpoint: 6 months progression-free survival (PFS-6) Secondary Objective: efficacy, safety, Secondary Endpoint: overall survival, objective response rate, adverse events	

Number of Subjects	Up to 27 subjects
Diagnosis and Main Inclusion Criteria	• Histologically proven unresectable or recurrent gastric or gastroesophageal adenocarcinoma • At least one prior chemotherapy regimen including a fluoropyrimidine and/or platinum agent • At least one line of treatment with a PD-1 or PD-L1 inhibitor in patients with PD-L1 CPS score >=10% • Age ≥ 18 years • Performance status (Eastern Cooperative Oncology Group) ≤ 2 • Adequate bone marrow function (ANC≥1000/mcL); and platelet count ≥ 60,000/mcL • Adequate liver function (total serum bilirubin level within normal institutional limits (or <3mg/dL in patients with Gilbert's disease) and serum transaminases ≤3xULN or ≤5xULN if liver metastasis is present); • Adequate renal function (serum creatinine level < 1.5xULN) • An expected survival period of>3 months • Patients with known MSI-High or dMMR tumors must have disease progression after at least one line of immunotherapy

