7.4 Reporting Requirements

Adverse events, serious adverse events, deviations, violations, and unanticipated problems must be entered into the clinical trial management system (CTMS), OnCore, and must also be reported to the following entities according to the timelines mentioned in the chart below. Serious adverse events collection will start at the time patient signs consent until 30 days after the end of treatment. Adverse events will be collected from the time the research patient begins treatment until 30 days after the end of treatment. All adverse events/serious adverse events should be followed until resolution or stabilization.

Event Type	Coordinating Center/Medical Monitor	UCI IRB	Exelixis, Inc.	CFCCC DSMB
Unanticipated Problem	Within 24 hours from date the site is aware of the event, the site should enter this information into OnCore. An email notification should also be sent via email to [contact] and [contact] .	Within 5 business days submit an Unanticipated Problem Report (UP). Current policy can be found here.	Within 1 business day of learning of the event. Submit a MedWatch Form to Exelixis via [contact]) or email ([contact]). All follow up information must be sent to Exelixis within 1 business day of PI's receipt of new information. Please refer to section 7.6 for further information.	Within 5 days from date PI is aware of the event. This information must be reported into OnCore.
AEs and SAEs (non- Unanticipated Problem)	Please refer to section 7.5 for reporting timeframes on AEs and SAEs	N/A	Please refer to section 7.6 for other reportable events	Please refer to section 7.5 for clarification on reporting timeframes for AEs and SAEs
Non-compliance	N/A	N/A	N/A	Please refer to section 7.5 for reportable deviations/violations
Serious or continuing non-compliance	Within 24 hours via email to [contact] and [contact]	Within 5 business days submit a New Information Report	N/A	Within 5 days from date PI is aware of the event.
Prospective/Planned Deviations	At least 5 business days prior to the event via email to [contact] and [contact] for approval.	At least 48 hours prior to date the request is needed by. Submit a Prospective Deviation Request form	N/A	At the time of progress review as aggregate reports

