9.0 STATISTICAL CONSIDERATIONS

9.1 Study Design/Study Endpoints

This is a single-arm, open label, phase-II trial designed as a pilot to see if the treatment regimen is worthy of further study. Specifically, the trial is designed as the first stage of a Simon two-stage, minimax design[39]. The goal is to gather evidence on efficacy or futility of the study treatment in this study population, while monitoring toxicity. The two-stage approach offers economy and exposes the fewest possible participants to potential harm without substantial benefit, with control of the probability of errors in decisions.

Primary Endpoint: For efficacy the primary endpoint is progression-free survival at six months (PFS-6), dating from the first dose of study treatment. Progression is defined and determined as given in Section 61.6. For toxicity, the primary endpoint is the number of participants showing serious toxicity during their participation in the trial. Serious toxicities are given in Section 7.0.

Efficacy Null Hypothesis: Based on current outcomes for this study population[25][26], the null hypothesis is that 5% of evaluable patients will be progression-free at six months.

Efficacy Alternative Hypothesis: Based on our clinical judgment and aspirations, we anticipate that 20% (or more) of evaluable participants will be progression-free at six months. In our view, 20% progression-free at six months is the smallest advance that would be judged clinically worthwhile.

Secondary endpoints:

- Overall survival, defined as time from starting treatment to death from any cause.
- Objective response rate in patients with measurable disease as defined in section 6.0
- Safety as described in the adverse events in section 7.0

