9.2 Sample Size and Accrual

Sample Size: Given null- and alternative-hypothesis proportions of 0.05 and 0.20, respectively, approximately 20 evaluable subjects will signal futility/efficacy with 80-percent power and five percent risk of type-I error. Under these conditions the table below gives the number of evaluable subjects required, the smallest number of patients progression-free at six months to signal efficacy, and the probability of correctly declaring futility.

Design Approach	Sample Size	Responses Signal Efficacy	Probability Correctly Asserting Futility
Minimax	19	>=2	0.75

As may be seen, the minimax approach requires 19 evaluable subjects for this project. If at least two participants are progression-free at six months, then the treatment regimen is considered worthy of further study. Given that result, then, in a separate study to complete stage two of the design, an additional eight evaluable subjects would be run. If at least four of the total of 27 evaluable were progression-free at six months that would be sufficient evidence to reject the null hypothesis of five percent in favor of the alternative hypothesis of 20 percent. The probability of declaring futility when in fact the null hypothesis (viz., 5%) is true is at least 75 percent.

No more than nine patients with PD-L1 CPS = 1-9% who are immunotherapy naïve will be enrolled.

Continuous Monitoring for Excess Toxicity: All participants in trial are monitored for serious toxicity for the duration of their participation in the study. Serious toxicities are given in Section 7. A sequential Pocock-type boundary will inform decisions to continue or stop accrual for excess toxicity, as accrual proceeds (Ivanova, 2005). The table below shows the cumulative number of participants enrolled and the corresponding cumulative number of serious toxicities that will signal the underlying risk of serious toxicity exceeds 33 percent (5% risk of type-1 error).

Threshold Number of Cumulative Toxicities that Signal Excess Toxicity as a Function of Cumulative Number Enrolled*

Cumulative	Threshold Number
Number	Showing Serious
Enrolled	Toxicity to Stop
	Accrual
1	-
2	-
3	-

CONFIDENTIAL

4	4
5	5
6	5
7	6
8	7
9	7
10	7
11	8
12	8
13	9
14	9
15	10
16	10
17	11
18	11
19	12
20	12

^{*} Pocock -type boundary with maximum acceptable probability of toxicity set to 33 percent and type-1 risk of five percent[40].

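### Section 9.2 reads the toxicity stopping table by number enrolled and does not keep earlier rows in force, so the boundary loses sensitivity and signals later than it could; counting in enrolment order is a cheap improvement.

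*Combined protocol and SAP*

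**What the plan says.** Section 9.2 (Continuous Monitoring for Excess Toxicity) states that "A sequential Pocock-type boundary will inform decisions to continue or stop accrual for excess toxicity, as accrual proceeds". It introduces the limits with the words "The table below shows the cumulative number of participants enrolled and the corresponding cumulative number of serious toxicities". The table is titled "Threshold Number of Cumulative Toxicities that Signal Excess Toxicity as a Function of Cumulative Number Enrolled" and runs from 1 to 20 patients, with limits from row 4 on. Its footnote describes a "boundary with maximum acceptable probability of toxicity set to 33 percent and type-1 risk of five percent".

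The counted event has no fixed window. Section 9.1 says that for toxicity "the primary endpoint is the number of participants showing serious toxicity during their participation in the trial", and Section 9.2 adds that "All participants in trial are monitored for serious toxicity for the duration of their participation in the study". Section 7.4 sets the collection period: "Adverse events will be collected from the time the research patient begins treatment until 30 days after the end of treatment".

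The plan does not say that n is limited to patients whose outcome is known, that accrual pauses while outcomes are pending, or that an earlier row is read again when one of its patients shows toxicity later.

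**The concern.** A continuous boundary of this kind is calibrated as if each patient's outcome were known when that patient is added to n. Here a patient adds to n on enrolment, but may show toxicity weeks or months later.

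An example from the printed limits: row 10 has limit 7 and row 11 has limit 8. Suppose seven of the first ten patients eventually have a serious toxicity, but the seventh event comes after patient 11 has enrolled and before patient 11 has had any event. Read against current enrolment, the count is 7 against a limit of 8, and there is no signal. Read against row 10, the boundary has been reached.

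At stake is how soon the plan's only numeric toxicity boundary signals when the regimen is too toxic. Section 9.1 gives limiting exposure to harm as a reason for the design.

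**Working it through.** **Inputs.** From Section 9.2: maximum acceptable rate p0 = 0.33, type-1 risk 5%, and limits for n = 4 to 20 of 4, 5, 5, 6, 7, 7, 7, 8, 8, 9, 9, 10, 10, 11, 11, 12, 12. The table ends at 20, so N = 20 is used, although the study summary allows "Up to 27 subjects".

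**Step 1: reproduce the plan's figure.** Let f_n(k) be the probability of k toxicities among n patients with no crossing so far, and t_n the limit in row n. Then f_n(k) = (1 − p) f_{n−1}(k) + p f_{n−1}(k − 1). Any mass at k ≥ t_n is moved to the crossing probability. At p = 0.33:

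- Row 4: 0.33^4 = 0.0119.
- Row 5: no new crossing, because at most 3 toxicities remain possible at n = 4.
- Row 6: three toxicities in the first four, then two more: 4 × 0.67 × 0.33^5 = 0.0105.
- Continued to row 20, the total is 0.0486.

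A Pocock-type boundary with one common pointwise level, p0 = 0.33 and N = 20 returns all 17 printed limits. The stated 5% is therefore reproduced, on the premise that all n outcomes in a row are known. The same recursion gives 0.377 at a true 50% and 0.698 at a true 60%.

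**Step 2: assumptions for delay.** The documents give neither accrual rate nor onset distribution. The study summary has a 3-year duration and follow-up of up to 18 months after the last enrolment. That leaves about 36 − 18 = 18 months of accrual, and 27 / 18 = 1.5 patients per month. A 3-month spread is a rough guess: the 2.0-month median PFS cited in Section 1.4 for single-agent pembrolizumab, plus the 30-day collection period. Wider ranges follow in step 4.

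**Step 3: base case.** Simulation with exponential inter-arrival times, 1.5 patients per month and onset uniform over 3 months:

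| Quantity | Outcomes known at once | Current-enrolment row | Enrolment order, all rows |
|---|---|---|---|
| Ever crosses, true 33% | 4.9% | about 2–2.5% | about 5% |
| Ever crosses, true 50% | 38% | 29% | about 38% |
| Ever crosses, true 60% | 70% | 63–64% | 70% |
| Crosses before patient 20 enrolled, true 60% | about 66% | about 47% | about 61% |
| Mean enrolled, true 60% | 13.1 | 16.5 | 14.8 |

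The ever-crosses rows include crossings after all 20 are enrolled, when the table has no accrual left to stop. The last two rows are therefore the relevant ones for exposure. The saving is 16.5 − 14.8 = 1.7 patients.

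**Step 4: range.**

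- At a true 33%, with 0.67 months between patients and uniform onset, the current-row reading crosses in about 3.7%, 3.0%, 2.3% and 1.4% of trials for spreads of 1, 2, 3 and 6 months. With slower accrual (0.95 months between patients) or front-loaded onset it reaches at most about 4.5% at a 1-month spread.
- At a true 60% and 1.5 patients per month, crossing before patient 20 is 62% against 66% for a 1-month spread (saving 0.6 patients) and 24% against 51% for a 6-month spread.
- With front-loaded onset over 3 months, mean enrolment is 15.4 against 14.3, a saving of 1.1.
- Over 1 to 3 patients per month and spreads of 1.4 to 6 months, the saving at a true 60% is about 0.6 to 2.1 patients.

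**Step 5: why enrolment order works.** If the current-row reading signals at n enrolled, those toxicities are all among the first n enrolled, so the row-n condition also holds. Enrolment order can never signal later. Once outcomes are complete, the count among the first n is the binomial count used in step 1, so the probability of ever crossing returns to the exact value whatever the onset pattern.

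**The case against.** The strongest objection is that the text does not force the unfavourable reading. Section 9.2 pairs the number enrolled with the *corresponding* number of toxicities, which can mean toxicities among those n patients, and nothing says that earlier rows lapse. That stands as an ambiguity. But the table title, the column label and the instruction to use the table as accrual proceeds all point to the row for current enrolment, and no sentence tells the user to go back.

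A reader might infer that the rule breaks its stated 5% error, or falls short of a promised power. The documents support neither. False stops at a true 33% are about 1% to 4.5% on the current-row reading, which is below 5%. No power, stopping probability at higher rates or expected enrolment is stated, so there is no promised sensitivity to miss.

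The size does depend on assumptions. Section 4.4 says many cabozantinib events come in the first few weeks, which favours a small effect. Section 7.1.2 gives later median onsets for pembrolizumab's immune-mediated events: hepatitis 1.3 months, pneumonitis 3.3, colitis 3.5, and nephritis 3.2 to 5.1. Onset is therefore mixed.

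The boundary is also not the only safeguard. It informs a decision, unexpected grade 3 to 5 serious events go promptly to the coordinating centre and the DSMB (Section 7.5), and the DSMB reviews aggregate safety (Section 10.5.2). Finally, enrolment-order counting does not settle what counts as a serious toxicity. These points limit the weight of the concern; they do not remove it.

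**Conclusion.** The point holds as a loss of sensitivity, not as an error-rate violation. The printed limits are correct for patients with known outcomes. Compared with the row for current enrolment, the same limits make the rule conservative and later to signal.

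Under the base-case assumptions the loss at a true 60% is about 14 percentage points in crossing before patient 20 (61 − 47) and about 1.7 patients in mean enrolment. It shrinks to roughly half a patient when toxicity appears within about a month. The direction follows from the logic of the rule and needs no assumption; the size rests on assumed accrual and onset. This is a cheap improvement rather than a defect that undermines the trial.

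**What to change.** Add to Section 9.2 that the boundary is crossed as soon as, for any row n up to the number enrolled, the number of patients with serious toxicity among the first n enrolled reaches the row-n limit, whenever those toxicities occur.

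This uses the same table and data and needs no observation window. The only statistical cost is that false stops at a true 33% rise from about 1–4.5% to the 5% already stated. The boundary would still inform the decision alongside DSMB review.

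One substitute should be avoided: counting toxicities as they occur while adding toxicity-free patients to n only at completion. That over-weights early events. With 1 month between patients, false stops rose to about 8% for a 3-month window and 14% for a 6-month window.

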9.3 Data Analyses Plans

The primary endpoint (PFS-6) will be calculated at 6 months after the last patient enrolled has started treatment, or at the time of progression of the last patient enrolled, whichever occurs first.

Participants will be characterized on host and demographic factors, with continuous measures given as means or medians and categorical measures given as percents. Consistent with the phase-II nature of the research, we will examine the data in many ways to illuminate future research priorities. We will estimate survival curves for progression-free and overall survival, and attempt to identify systematic differences between those who respond to treatment and those who do not. Survival will be estimated by Kaplan-Meier methods. If assumptions are met, we will model survival using Cox proportional- hazards, eliminating ties by subtracting a small, randomly generated amount from the observed times[41]. As may be indicated, we will transform data to correspond better to analytic requirements, using logit transforms for percent data[42] and log or some other approach for continuous measures. As the goals of these secondary analyses are to inform decisions about future research, no formal statistical hypothesis-testing will be done, probabilities from statistical tests will augment clinical judgment in interpretation, and we will not regard overall, study-wise, error rates for these secondary analyses.

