Study Product(s), Dose, Route, Regimen	Cabozantinib 40 mg p.o. daily days 1-21 Pembrolizumab 200 mg i.v. day 1 every 21 days
Study Duration	The study will consist of a screening period of up to 28 days, a treatment period (21 day cycles), and a follow up period of up to 18 months after enrollment of the last patient or until death, whichever occurs first. Subjects will be allowed to continue treatment on study until disease progression, unacceptable toxicity or withdrawal of consent.
Statistical Methodology	Main objective is to estimate the efficacy of the combination regimen with PFS-6 as a primary endpoint. The null hypothesis in this heavily pretreated population is a PFS-6 of 5%. The alternative hypothesis assumes a PFS-6 of 20% or more. A 2-stage approach will be used. If PFS-6 is seen in at least 2 out of the first 19 patients, the cohort will be expanded to a total of 27 patients. If the PFS-6 is achieved in at least 4 patients in the expanded cohort, that would be sufficient evidence to reject the null hypothesis of 5% in favor of the alternative hypothesis of 20% or more.

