4.8 Removal of Patients from Protocol Therapy

Patients will be removed from therapy when any of the criteria listed in Section 5.6 apply. Notify the Principal Investigator via email ([contact] and [contact]), and document the reason for study removal and the date the patient was removed in the Case Report Form. The patient should be followed-up per protocol.

4.9 **Patient Replacement**

Patients will not be replaced

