5.3.3 Tumor Assessments

 To be completed every 8 weeks (+/- one week) during first year of treatment and every 3 months (+/- one week) after the first year until patient comes off study

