6.1.1 Definitions

Evaluable: All patients receiving cycle 1, day 1 of the protocol treatment.

Evaluable for toxicity. All patients will be evaluable for toxicity from the time of their first treatment with study drug.

Evaluable for objective response. Only those patients who have measurable disease present at baseline, have received at least one cycle of therapy, and have had their disease re-evaluated will be considered evaluable for response. These patients will have their response classified according to the definitions stated below. (Note: Patients who exhibit objective disease progression prior to the end of cycle 1 will also be considered evaluable.)

Evaluable Non-Target Disease Response. Patients who have lesions present at baseline that are evaluable but do not meet the definitions of measurable disease, have received at least one cycle of therapy, and have had their disease re-evaluated will be considered evaluable for non-target disease. The response assessment is based on the presence, absence, or unequivocal progression of the lesions.

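### Section 9.3 lets the primary count be made when the last-enrolled patient progresses, before other recent enrolees have reached six months from their own first dose

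*Combined protocol and SAP*

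**What the plan says.** Section 9.3 gives two possible dates for calculating the primary endpoint and takes the earlier. The first is six months after the final patient begins treatment. The second is "or at the time of progression of the last patient enrolled, whichever occurs first".

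Section 9.1 defines the endpoint patient by patient: "progression-free survival at six months (PFS-6), dating from the first dose of study treatment". The decision rules in Section 9.2 are counts. For stage 1: "If at least two participants are progression-free at six months, then the treatment regimen is considered worthy of further study". For the full design: "If at least four of the total of 27 evaluable were progression-free at six months".

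Section 6.1.1 defines evaluable patients as "All patients receiving cycle 1, day 1 of the protocol treatment", and Section 4.9 adds "Patients will not be replaced".

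The documents disagree on whether the last eight patients belong to this trial. Section 9.2 places them in a separate study. The Statistical Methodology entry of the Study Summary places them in this one: "If PFS-6 is seen in at least 2 out of the first 19 patients, the cohort will be expanded to a total of 27 patients". So the final patient in Section 9.3 could be patient 19 or patient 27.

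**The concern.** The first date is sound: once the final patient has six months of follow-up, so has everyone who started earlier. The second is not, because one patient's progression says nothing about the others. Someone who began two months before the final patient, and is still progression-free when that patient progresses at week 8, has about four months of follow-up and cannot yet be called progression-free at six months.

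Nothing in the documents makes the calculation wait for such patients or says how to class them. They cannot be set aside either, since anyone who received the first dose is evaluable and there is no replacement. They occupy a place in the 19 or 27 without being able to count as a success. With thresholds of 2 and 4, losing one or two eventual successes can turn an active regimen into an apparent failure.

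**Working it through.** **1. Reproduce the design.** Inputs from Sections 9.1 and 9.2: null 5%, alternative 20%, continue if at least 2 of 19, reject the null if at least 4 of 27. Let b(k; n, p) be the binomial probability.

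- Stopping at stage 1 under 5%: 0.95^19 + 19 × 0.05 × 0.95^18 = 0.3774 + 0.3774 = 0.755 (Section 9.2 states 0.75).
- Passing 2 of 19 under 20%: 1 − 0.8^19 − 19 × 0.2 × 0.8^18 = 1 − 0.0144 − 0.0685 = 0.917.
- Rejection probability: b(2; 19, p) × P(at least 2 of 8) + b(3; 19, p) × P(at least 1 of 8) + P(at least 4 of 19).
  - At 20%: 0.1540 × 0.4967 + 0.2182 × 0.8322 + 0.5449 = 0.803 (stated 80% power).
  - At 5%: 0.1787 × 0.0572 + 0.0533 × 0.3366 + 0.0132 = 0.041 (stated limit 5%).

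With every patient's six-month status known, the plan's figures hold.

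**2. How often the early date applies.** It applies whenever the final patient fails before six months: 1 − 0.20 = 80% of trials at the alternative and 1 − 0.05 = 95% at the null. No accrual assumption is needed.

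**3. An example.** Section 5.3.3 schedules scans as follows: "To be completed every 8 weeks (+/- one week) during first year of treatment". If the final patient progresses at the first scan (8 weeks, 1.84 months), everyone who started in the preceding 6 − 1.84 = 4.16 months is short of six months. That is about 4 patients at 1 per month and about 6 at 1.5 per month, less those who have already progressed.

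**4. Effect on the decision.** Assumptions:
- PFS is exponential, with hazard −ln(p)/6 per month, and progression is dated continuously.
- Accrual is Poisson at 0.5, 1, 1.5 or 2 patients per month. The documents state no rate.
- The cut-off is the final patient's start plus the smaller of six months and that patient's time to progression.
- A patient other than the final one is undetermined if progression-free at the cut-off with under six months of follow-up, and is then not counted as a success.
- For the 27-patient rule, all 19 stage-1 patients have known status before patient 20 enters. No section states such a pause.

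Simulation gives:

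| Accrual per month | 0.5 | 1 | 1.5 | 2 |
|---|---|---|---|---|
| 19 patients, 20%: at least one eventual success left out | about a quarter | 40% | 51% | 58% |
| 19 patients, 20%: passes 2 of 19 (full follow-up 0.92) | 0.88 | 0.83 | 0.76 | 0.68 |
| 19 patients, 5%: passes 2 of 19 (full follow-up 0.245) | 0.207 | 0.172 | 0.139 | 0.111 |
| 27 patients, 20%: at least one eventual success left out | 24% | 40% | 49% | 53% |
| 27 patients, 20%: power (full follow-up 0.80) | 0.76 | 0.72 | 0.68 | 0.66 |
| 27 patients, 5%: type-I error (full follow-up 0.041) | 0.034 | 0.028 | 0.024 | 0.021 |

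For orientation, suppose the 3-year duration in the Study Summary includes the 18 months of follow-up. Then 18 months remain for accrual, 19/18 is about 1.06 per month, and the chance of passing 2 of 19 is 0.82. That rate is inferred, not stated.

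**The case against.** **The early date is common, but harm is less so.** This stands. The 80% and 95% are simply the final patient's own failure rates. A reader might take them as the share of trials damaged, but damage needs an eventual success to be left out, and its size depends on accrual. At 0.5 per month the 27-patient power loss is only 4 points.

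**The error is conservative and the trial is a pilot.** This also stands. A reader might infer a raised false-positive risk, since counting undetermined patients as progression-free would put the 27-patient type-I error at 0.07/0.10/0.12/0.14. The documents do not support that count: Sections 9.1 and 9.2 require six months from first dose. The risk is a false futility call.

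**Patients stay under observation, so the count could be completed later.** The data would exist, but Section 9.3 fixes the earlier date. Waiting would depart from the written plan after results are visible in an open-label, single-arm trial.

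**Kaplan-Meier handles short follow-up.** Section 9.3 names it for survival curves, whereas the decision rule in Section 9.2 is a count.

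**Progression is seen only at scans.** Fair, and it changes the baseline. If status is dated by scan throughout at the same hazards, the week-24 scan is the last before six months. Documented PFS-6 becomes about 0.228 and 0.064 instead of 0.20 and 0.05. Power with full follow-up is then 0.88 with type-I error 0.085, and the early cut lowers power to 0.86/0.83/0.80/0.78. The loss remains. A reader might conclude that the calculation should also wait for a scan after six months, but which scan defines six-month status is a separate endpoint question that this defect does not settle.

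**Conclusion.** The concern holds. As written, Section 9.3 permits the primary count while some patients in the denominator have no six-month status, and no other section corrects this. That follows from the text alone; only its size rests on assumptions.

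If Section 9.2 governs and this trial ends at 19 patients, the loss in the chance of passing at a true 20% runs from about 4 points at 0.5 per month to about 24 points at 2 per month. If the Study Summary governs and the trial expands to 27, the power loss runs from about 4 to about 14 points, given a mature stage 1. Both ranges assume exponential PFS, continuous dating and undetermined patients not counted as successes. The direction is toward declaring an active regimen futile, with no inflation of type-I error on the plan's own definition.

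**What to change.** In Section 9.3, delete "or at the time of progression of the last patient enrolled, whichever occurs first" and replace the timing sentence with text such as:

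*PFS-6 will be calculated once every treated patient has progressed, died, or completed six months from their own first dose; the same condition applies to the count in the first 19 patients.*

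The cost is one clause deleted and one sentence reworded. The analysis comes at most six months later than under the present wording, well within the follow-up planned in Section 4.7, which runs to 18 months after the last enrolment. The design's own figures (early stopping 0.755, type-I error 0.041, power 0.803) are then restored, provided that 5% and 20% are the PFS-6 rates as actually counted.

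The change does not settle which scan establishes six-month status, or how patients with missing assessments are counted; those need their own statements. The conflict between Section 9.2 and the Study Summary over the last eight patients should also be resolved, so that the final patient is unambiguous.
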